Preliminary pharmacokinetic (PK) analysis from the ongoing FIH study suggests dose-related increases in free AMG 427 maximum observed concentration (C_{max}) and area under the concentration-time curve (AUC). Preliminary geometric mean terminal half-life estimates range from 0.6 to 2.1 days over the evaluated range of doses up to [REDACTED] $\mu\text{g}/\text{day}$. Higher doses and exposures may be needed to provide thorough coverage of predicted minimally efficacious exposures estimated from in vitro AMG 427-mediated cell cytotoxicity in FLT3-expressing AML cell lines.

The emerging clinical safety and PK data from the ongoing FIH study support the exploration of additional dose levels ([REDACTED] μg) in the dose escalation part of the study to determine the MTD for AMG 427.

Recommendations to explore additional dose levels will be made by the Dose Level Review Team (DLRT) following review of the PK, safety, and efficacy data for each enrolled cohort.

Amendment 4

Protocol Title: A Phase 1 First-in-human Study Evaluating the Safety, Tolerability, Pharmacokinetics, Pharmacodynamics and Efficacy of AMG 427 in Subjects With Relapsed/Refractory Acute Myeloid Leukemia

Amgen Protocol Number (AMG 427) 20170528

Amendment Date: 17 February 2020

Rationale:

The protocol is being amended according to guidance provided by Food and Drug Administration (FDA).

Amendment 3

Protocol Title: A Phase 1 First-in-human Study Evaluating the Safety, Tolerability, Pharmacokinetics, Pharmacodynamics and Efficacy of AMG 427 in Subjects With Relapsed/Refractory Acute Myeloid Leukemia

Amgen Protocol Number: AMG 427 20170528

Amendment Date: 26 November 2019

Rationale:

The following updates were made to the protocol, dated 08 June 2018:

- New dosing schedule with an additional Day 3 infusion to current dosing regimen. Addition made based on pharmacological data, in order to provide sustained exposure of AMG 427 above the predicted minimally efficacious exposure for the entire treatment cycle.
- Schedule of assessments updated to include bone marrow assessments at safety follow-up and long-term follow-up visits where applicable
- Disease-related events and all associated references were removed for the purpose of adherence to current Amgen SOPs
- Reference to self-evident corrections (SEC) were removed for the purpose of adherence to current Amgen SOPs
- Update to References section
- Minor corrections and clarifications throughout
- Addition of Substudy adding Enbrel (etanercept) as pre-medication, in order to explore better safety, tolerability, and efficacy of BiTE therapy.

Amendment 2

Title: A Phase 1 First-In-Human Study Evaluating the Safety, Tolerability, Pharmacokinetics, Pharmacodynamics and Efficacy of AMG 427 in Subjects With Acute Myeloid Leukemia

AMG 427

Amgen Protocol Number 20170528
IND number BB-IND 138440

Amendment Date: 30-April-2019

Rationale:

This protocol is being amended to allow for the enrollment of AML subjects with measurable/minimal residual disease (MRD).

The following changes were made to the original protocol, dated 08 June 2018:

- References to “Relapsed/Refractory” in the protocol title and in relevant sections of the protocol were removed to indicate that subjects with relapsed/refractory AML as well as subjects with measurable/minimal residual disease (MRD)-positive AML will be evaluated in this trial
- Statistical considerations updated to account for MRD-positive AML subjects
- Schedule of assessments updated to include bone marrow assessments at safety follow-up and long-term follow-up visits where applicable
- Disease-related events and all associated references were removed for the purpose of adherence to current Amgen SOPs
- Reference to self-evident corrections (SEC) were removed for the purpose of adherence to current Amgen SOPs
- Update to References section
- Minor corrections and clarifications throughout

Amendment 1

Title: A Phase 1 First-In-Human Study Evaluating the Safety, Tolerability, Pharmacokinetics, Pharmacodynamics and Efficacy of AMG 427 in Subjects With Relapsed/Refractory Acute Myeloid Leukemia

AMG 427

Amgen Protocol Number 20170528
IND number BB-IND 138440

Amendment Date: 08 June 2018

Rationale: This protocol is being amended based on comments received from the FDA upon submission of the US IND on April 9, 2018. All updates are in line with changes requested by the agency.

The following changes were made to the original protocol, dated 22 March 2018:

- Eligibility criteria was revised to include patients who have failed treatment with, are intolerant to, or are not candidates for available therapies for treatment of relapsed or refractory AML
- Dose Limiting Toxicity (DLT) window will start on D1 (start of the administration of the first infusion) and last for 28 days for all cohorts.
- Confirmed Hy's Law cases will be included as DLTs.
- Subjects experiencing a Grade 4 adverse event during infusion will be permanently discontinued from investigational product
- Dosing instructions for tocilizumab are updated such that subjects can be given up to 3 additional doses of tocilizumab, 8 hours apart, if needed.
- Cohort size in dose expansion is modified to n=6
- Early stopping rules and efficacy futility rules have been implemented in dose expansion phase based on DLT criteria; enrollment to dose expansion will be paused or possibly terminated if these rules are met. Secondary endpoint (efficacy parameters) has been updated to reflect the efficacy futility rules.
- Adverse events will be recorded starting from the time of consent, rather than from the time of dosing. Schedule of events was updated to reflect this change.
- Statement added to indicate that FDA will be provided with brief interim results of the dose escalation phase once MTD and RP2D is established.
- Clarifications/minor corrections to Schedule of Assessments

Approved

**List of Figures**

## List of Abbreviations

Abbreviation	Explanation
AML	Acute Myeloid Leukemia
AUC	Area under concentration time curve
C max	maximum observed concentration
CRF	case report form
CRS	Cytokine Release Syndrome
DLRM	dose level review meeting
DLT	dose limiting toxicity
ECG	Electrocardiogram
eCRF	electronic case report form
end of study for individual subject	defined as the last date that protocol-specified procedures are conducted for an individual subject
end of treatment	defined as the date of final assessment for the protocol specified treatment phase of the study for an individual subject
end of study (primary completion)	defined as the date when the last subject is assessed or receives an intervention for the purposes of final collection of data for the primary endpoint(s).
FIH	First in Human
Ig	Immunoglobulin
ICF	informed consent form
IP	Investigational Product
MRD	Minimal/measurable Residual Disease
NA	Not Applicable
PD	Pharmacodynamic
PK	Pharmacokinetic
PR	the interval measured from the beginning of the P wave to the beginning of the QRS complex in the heart's electrical cycle as measured by electrocardiogram
QRS	the interval between the Q wave and the S wave in the heart's electrical cycle as measured by electrocardiogram; represents the time it takes for depolarization of the ventricles
QT	measure of the time between the start of the Q wave and the end of the T wave in the heart's electrical cycle as measured by electrocardiogram
QTc	QT interval corrected for heart rate using accepted methodology
RFS	Relapse Free Survival
R/R	Relapsed/Refractory

study day 1	defined as the first day that protocol specified investigational product is administered to the subject
$t_{max}$	time to maximum concentration

## 1. Introduction

The purpose of this Statistical Analysis Plan (SAP) is to provide details of the statistical analyses that have been outlined within the protocol amendment 7 for study 20170528, AMG 427 dated **16 March 2022**. The scope of this plan includes the interim analysis, the primary analysis and the final analysis that are planned and will be executed by the Amgen Global Biostatistical Science department unless otherwise specified. PK, PD/biomarker analyses will be provided by Clinical Pharmacology, Modeling and Simulation (CPMS) group and clinical biomarker group in Department of Translational Medicine, respectively. Separate SSAP will be created to prespecify additional analysis required to support assessment of an alternative for prophylaxis of cytokine release syndrome (CRS), the main on-target toxicity identified for AMG 427, in schedule B, in subjects with R/R AML.

## 2. Objectives, Endpoints and Hypotheses

[figure not shown]
### 2.1 Objectives and Endpoints

[figure not shown]
Objectives	Endpoints
Primary	

• Evaluate the safety and tolerability of AMG 427 in adult subjects with relapsed/refractory (R/R) AML or minimal/measurable residual disease-positive (MRD+) AML

• Estimate the maximum tolerated dose (MTD) and / or a biologically optimal dose (eg, recommended phase 2 dose [RP2D])

• Evaluate the safety and tolerability of extended intravenous (eIV) administration of AMG 427

	

• Safety: Dose-limiting toxicities (DLTs), treatment-emergent adverse events (TEAEs) and treatment-related adverse events (TRAEs)

Secondary	

Characterize the pharmacokinetics (PK) of AMG 427

	

AMG 427 PK parameters including, but not limited to, maximum serum concentration (<math>C_{max}</math>), minimum serum concentration (<math>C_{min}</math>), area under the concentration-time curve (AUC), and if feasible, half-life (<math>t_{1/2}</math>) of AMG 427

Evaluate the anti-leukemia activity of AMG 427

	

Efficacy parameters for (R/R) AML: Subject response to treatment with AMG 427 (response defined as complete response/remission [CR] / complete response/remission with incomplete recovery of peripheral blood counts [CRi] / morphologic leukemia-free state, partial remission [per modified International Working Group (IWG) criteria], complete response/remission with partial hematologic recovery [CRh]) and duration of response (duration of response will only be measured for subjects in the expansion cohort).

Efficacy parameters for MRD+ AML: Subject response to treatment with AMG 427 (response refers to conversion from MRD + status to MRD - status), relapse free survival,

	
and overall survival (relapse free survival and overall survival will only be measured for subjects in expansion cohort).

--	--

Exploratory

## 2.2 Hypotheses and/or Estimations

AMG 427 will demonstrate evidence of anti-leukemic activity at a safe and well-tolerated dose in subjects with **MRD+ or R/R AML**.

## 3. Study Overview

### 3.1 Study Design

This is a First in Human (FIH), open-label, phase 1 dose escalation study. AMG 427 will be administered as a short **intravenous (IV) infusion (eIV infusion may apply)** in adult subjects with **MRD+ or R/R AML**. The study will be conducted at approximately 15 sites in the US, Australia, Canada, Japan, South Korea, and Germany. Additional countries or sites may be added if necessary.

The study will consist of up to a 14-day screening period, a treatment period, a safety follow-up period (SFU), and a long-term follow-up (LTFU) period (for subjects enrolled in the dose expansion phase only).

The dose-escalation cohorts will estimate the MTD, safety, tolerability, PK, and **pharmacodynamics (PD)** of AMG 427 in subjects with **MRD+ or R/R AML** using a Bayesian logistic regression model (BLRM: [Neuenschwander et al, 2008](#)). Planned dose levels (dose per infusion) for the dose-escalation cohorts are as follows [REDACTED]

[REDACTED] µg.

**Additionally, an option for cohort escalation will be available for confirming the safety in Japanese population, at sponsor discretion, for up to a maximum of 6 subjects. The sponsor will notify Japanese sites, if applicable, when the extended slots for a cohort are open for enrollment (after the Dose Level Review Team [DLRT] has confirmed the dose level is safe). The starting dose for the [REDACTED]**

cohort will be [REDACTED] µg administered as short term IV infusions on day 1 (D1) and day 5 (D5). The doses administered for the cohorts following cohort [REDACTED] will be recommended by the Dose Level Review Team (DLRT). The initial several cohorts will receive 2-3 doses (1 each on D1, D3 [if applicable], and D5, **and D8 [if applicable]**). After reviewing the emerging PK, safety and efficacy data, the DLRT may recommend the administration of an additional **doses** on D3 **and D8**, to comprise a 2-week cycle with doses on D1/D3/D5/D8. At completion of the dose escalation cohorts, additional subjects (approximately **90 subjects, with approximately 40 subjects in the FIH cohorts and 50 subjects in the MRD+ cohorts**) will be enrolled in a dose expansion cohort to gain further clinical experience, safety, and efficacy data in subjects administered AMG 427.

The study will consist of 3 groups:

- **FIH Group: AMG 427 administered as short term IV infusions in R/R AML subjects.**
  - **(CLOSED) Etanercept (Enbrel) substudy: Etanercept will be administered for CRS prophylaxis 2 days prior to each cycle of AMG 427 short term IV infusions in R/R AML subjects in the US. (Etanercept may be implemented to FIH expansion groups based on emerging data).**
- **eIV Infusion Group: AMG 427 eIV infusions administered on days 1 and 2, and 3, with short term IV infusions on days 5 and 8 in R/R AML subjects. (eIV infusion may be implemented to FIH expansion groups based on emerging data).**
- **MRD+ Group: AMG 427 administered in short term IV infusions in MRD+ AML subjects.**

The study will have three alternative dosing schedules:

[figure not shown]
- Schedule A: - **CLOSED**
  - D1/D5 or D1/D5/D12/D19 (dexamethasone prophylaxis)
- Schedule B: **Etanercept Substudy (R/R AML) - CLOSED**
  - D1/D5 or D1/D5/D12/D19 (etanercept 2 days prior to each cycle) Etanercept (Enbrel) substudy used etanercept 2 days prior to infusion of each cycle D1, and if applicable, 2 days prior to infusion on D12. [REDACTED].
- Schedule C: **(Protocol Table 16 through Table 21) FIH, eIV (R/R AML), and MRD+ Group (MRD+ AML)**

- D1/D3/D5/**D8** or D1/D3/D5/**D8**/D12/D19 (dexamethasone prophylaxis)

**Note:**

- **The MRD+ group will use Schedule C for all cycle collections and Table 22 (from protocol) for additional whole blood MRD collection, or Table 23 (from protocol), as applicable.**

After reviewing additional PK, safety, and efficacy data, the DLRT may recommend the administration of additional **doses** on day 12 and day 19, to comprise a 4-week cycle with doses on either D1/D5/D12/D19 or D1/D3/D5/**D8**/D12/D19. Once the DLRT recommends a 4 or 6 dose schedule (D1/D5/D12/D19 or D1/D3/D5/**D8**/D12/D19), all subsequent cohorts will be treated with a 4 or **6** dose schedule. If on Schedule A (**CLOSED**) or C, all subjects will be pre-treated with an 8-mg dose of IV dexamethasone within 1 hour prior to D1, D3 (if applicable), and D5, **and D8 (if applicable)** AMG 427 doses and each dose step. A dose step is any AMG 427 dose that is higher for a given subject than the subject has previously received. A dose step will be triggered by the observation of CRS or infusion/**injection** related reaction at the first dose (see example in [Figure 1](#)). Dose steps may occur at the D3, D5, **D8**, D12 or D19 infusions. Each cycle will last for approximately 14 days for cohorts receiving 2 or 4 doses (D1/D5 or D1/D3/D5/**D8**), and approximately 28 days for cohorts receiving 4 or **6** doses (D1/D5/D12/D19 or D1/D3/D5/**D8**/D12/D19). Subjects will be assessed for DLTs for 28 days. Cycle will be followed by a treatment-free interval for 1-2 weeks (depending on response), which may be extended for up to 7 weeks or longer for the cohorts at higher doses, based on a dose level review meeting (DLRM) recommendation. The D3, D5, **D8 doses**, and the D12 and D19 **doses** (if applicable) may be at the same dose as the preceding **dose** or may be at a higher dose level (dose step). This will be based on tolerability of the lower dose level and other clinical signs, pharmacological, and PD results and will be recommended by the DLRT. For a schematic description of the different dose step options see [Figure 1](#). For logistical reasons, there is a  $\pm$  1-3 day window for dosing days.

#### Dose Escalation Cohorts

Dose escalation will be conducted in 2 stages: a single subject stage and a multiple subject stage. Single subjects will be enrolled at initial dose levels. Multiple subject cohorts, which will enroll 2 - 4 subjects per cohort, will be triggered by any evidence of pharmacologic activity, including, but not limited to infusion reactions, CRS, tumor lysis syndrome (TLS), or depletion of peripheral blasts and/or white blood cells. The Bayesian logistic regression model (BLRM) design will be used to guide dose escalation. The actual dose selected at each dose cohort may be at or below the model's recommended dose as determined by the DLRT after considering all information. Subjects will be assessed for DLTs for 28 days. Subjects in the etanercept (Enbrel) substudy (**CLOSED**) can intra-subject dose escalate after 1 cycle to the first-in-human (FIH) study (eg, move from schedule B to schedule C), if subjects show evidence of disease progression after discussion with the Sponsor (eg, use of hydroxyurea to control increasing WBC). Subjects who complete the DLT period may proceed to a higher dose level for the following treatment cycle once the next dose cohort has been deemed safe by the DLRT, after consultation with the Sponsor, if no DLT was reported during or after the completion of the DLT period for that subject.

#### Estimation of initial and target MTDs

It is anticipated that 2 to 3 MTDs may be estimated: 1 for the initial dosing and 1 - 3 for the subsequent dosing. Should the initial dose be limited by adverse events related to first dose effects and/or cytokine release syndrome, the second MTD (dose step) for the target dose will be estimated after giving the initial dose at MTD1. Each MTD will be estimated following the dose escalation guided by BLRM described above. A second

[figure not shown]
dose step may also be implemented in a cycle if this was considered appropriate and necessary to allow further dose escalation. This second dose step would be performed the same way as described above. In this case, a third MTD would be estimated for the dose to be administered after the second dose step.

Once the dose escalation phase has determined a final MTD, tocilizumab may be evaluated as an alternative prophylaxis to prevent / reduce the severity of CRS. A cohort of 3 subjects may be treated with AMG 427 at the final MTD dose level and a single dose of 8 mg/kg IV tocilizumab will be administered prior to the dose of AMG 427 replacing pretreatment with dexamethasone. If no DLTs are observed, 3 additional subjects will be included in this cohort. The use of tocilizumab may be further explored based on observed tolerability and other clinical and pharmacological data.

#### Expansion Cohort

At completion of the dose escalation cohorts, **approximately 90 additional subjects (approximately 40 R/R AML subjects in the FIH cohorts and 50 MRD+ AML subjects in the MRD+ cohorts)** will be enrolled in a dose expansion cohort to gain further clinical experience, safety, and efficacy data in subjects administered AMG 427. The dose to be evaluated will be at or below the MTD estimated in the dose escalation cohorts. Based on emerging safety data, the planned dose level and dose schedule may be modified during the conduct of the expansion phase. Additionally, enrollment to dose expansion will be paused and possibly terminated if safety stopping rules and/or efficacy futility rules are met. A final estimate of the MTD and RP2D will be evaluated and confirmed utilizing all DLT-evaluable subjects from the dose escalation and the dose expansion cohorts.

## Study Design and Treatment Schema

### 3.2 Sample Size

It is anticipated that approximately **200** subjects will be enrolled in this study, **with** approximately **110** subjects enrolled in the dose escalation cohorts and **90** subjects in the dose expansion cohort:

#### Dose escalation cohorts:

- **FIH (R/R AML): approximately 90 subjects**
  - **(CLOSED) etanercept substudy (R/R AML): approximately 25 subjects**
- **eIV (R/R AML): approximately 10 subjects**
- **MRD Group (MRD+): approximately 10 subjects**

#### Dose expansion cohorts:

- **FIH (R/R AML): approximately 40 subjects**
- **MRD Group (MRD+): approximately 50 subjects**

The sample size in the dose escalation is based on practical considerations and is consistent with conventional oncology studies with the objective to estimate the MTD.

With 2 subjects per cohort, there is a 19% to 55% probability of observing at least 1 DLT. With 3 subjects per cohort, there is a 27% to 70% probability of observing at least 1 DLT if the true DLT rate is 10% to 33% and with 4 subjects per cohort, there is a 34% to 80% probability.

In the dose expansion cohort, a subject number of 40 will provide an 87% probability of observing at least 1 adverse event with 5% incidence rate and 99% probability of observing at least 1 adverse event with 10% incidence rate. **A subject number of 50 will provide a 92.3% probability of observing at least 1 adverse event with 5% incidence rate and 99.5% probability of observing at least 1 adverse event with 10% incidence rate.** These probabilities will be 64% and 88% respectively with a subject number of 20. An exact 80% binomial confidence interval (CI) will be provided for response rate. With the 20 subjects and 20% response rate, the expected 80% CI would be 9% to 36%. With 40 subjects and 20% response rate, the expected 80% CI would be 12% and 30%. **With 50 subjects and a 40% response rate, the expected 80% CI would be 30.6% and 50.1%.**

### 3.3 Adaptive Design

The dose-escalation cohorts will estimate the MTD, safety, tolerability, PK and PD of AMG 427 in subjects with MRD+ or R/R AML using a Bayesian logistic regression model (BLRM: [Neuenschwander et al, 2008](#)). See Protocol Appendix H for the description of the two-parameter BLRM design.

During dose expansion, Amgen will conduct evaluations of the ongoing DLT event rate and the ongoing overall response rate.

#### **Safety Stopping Rules during Dose Expansion:**

During dose expansion, Amgen will conduct evaluations of the ongoing DLT event rate to assess if the threshold for pausing enrollment has been reached. If these stopping rules are met, then enrollment to the dose expansion will be paused pending a review of safety data and available pharmacokinetic, pharmacodynamics, and efficacy data by the DLRT. This review may result in early termination of the study, notification to Health Authorities, or may result in re-initiation of enrollment. The DLRT may implement additional measures, as appropriate, to reduce the risk of toxicity or to adapt and manage the toxicity. The stopping rules to pause enrollment use a Bayesian approach proposed by [Thall, et al \(1995\)](#); enrollment to dose expansion will be halted if the posterior probability that the DLT event rate is greater than 20% is > 80%. The stopping boundaries assuming a prior distribution of Beta (0.40, 1.60) are presented in [Table 1](#)

and the operating characteristics with pre-specified batch size of 6 new subjects per batch are presented in [Table 2](#). The evaluations could occur more frequently if necessary to address emerging safety concerns.

**Table 1. Stopping Boundary for Dose Expansion With Posterior Probability of 80% DLT Limit of 20%**

Number of subjects	Pause study enrolment if observing the number of these many DLT events
6	≥ 3
12	≥ 4
18	≥ 6
24	≥ 7
30	≥ 9
36	≥ 10
40	R/R AML expansion cohort completes
42	≥ 11
48	≥ 13
50	MRD+ AML expansion cohort completes

AML = acute myeloid leukemia, MRD+ = minimal/measurable residual disease-positive, R/R = relapsed/refractory.

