10.3 Adaptive Design

During dose expansion, Amgen will conduct evaluations of the ongoing DLT event rate and the ongoing overall response rate.

Safety Stopping Rules during Dose Expansion:

During dose expansion, Amgen will conduct evaluations of the ongoing DLT event rate to assess if the threshold for pausing enrollment has been reached. If these stopping rules are met, then enrollment to the dose expansion will be paused pending a review of safety data and available pharmacokinetic, pharmacodynamics, and efficacy data by the DLRT. This review may result in early termination of the study, notification to Health Authorities, or may result in re-initiation of enrollment. The DLRT may implement additional measures, as appropriate, to reduce the risk of toxicity or to adapt and manage the toxicity. The stopping rules to pause enrollment use a Bayesian approach proposed by [Thall, et al \(1995\)](#); enrollment to dose expansion will be halted if the posterior probability that the **DLT** rate is greater than 20% is $> 80\%$. The stopping boundaries assuming a prior distribution of Beta (0.40, 1.60) are presented in [Table 26](#) and the operating characteristics with pre-specified batch size of 6 new subjects per batch are presented in [Table 35](#). The evaluations could occur more frequently if necessary to address emerging safety concerns.

Table 26. Stopping Boundary for Dose Expansion With Posterior Probability of 80% DLT Limit of 20%

Number of subjects	Pause study enrollment if observing the number of these many DLT events
6	≥ 3
12	≥ 4
18	≥ 6
24	≥ 7
30	≥ 9
36	≥ 10
40	R/R AML expansion cohort completes
42	≥ 11
48	≥ 13
50	MRD+ AML expansion cohort completes

AML = acute myeloid leukemia, MRD+ = minimal/measurable residual disease-positive,
 R/R = relapsed/refractory.

Table 27. Operating Characteristics With Batch Size of 6 Subjects

True DLT rate	R/R AML		MRD+ AML	
	Probability of early stopping of dose expansion	Average dose expansion sample size*	Probability of early stopping of dose expansion	Average dose expansion sample size*
0.10	3.8%	38.9	3.9%	48.5
0.20	34.0%	31.5	37.8%	37.8
0.25	58.2%	25.6	64.9%	29.4
0.30	78.9%	19.9	85.5%	21.6
0.35	91.6%	15.4	95.7%	16.0
0.40	97.4%	12.2	99.1%	12.3
0.50	99.9%	8.7	100%	8.7

AML = acute myeloid leukemia, MRD+ = minimal/measurable residual disease-positive,
 R/R = relapsed/refractory.

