**Siltuximab Safety Stopping Rules:**

Amgen will conduct evaluations of the treatment and outcome of the CRS events treated with siltuximab on an ongoing basis to assess if the threshold for pausing siltuximab treatment has been reached as outlined in the table below. If these stopping rules are met, an adhoc DLRM will be triggered to review safety data and available pharmacokinetic, pharmacodynamics, and efficacy data. If recommended by DLRT, the use of siltuximab will resume. The stopping rules to trigger an adhoc DLRM to review siltuximab treatment use a Bayesian approach proposed by [Thall, et al \(1995\)](#); an adhoc DLRM will be triggered if the posterior probability that the CRS progression to Grade 3 rate is greater than 20% is  $> 80\%$  or the posterior probability that the CRS progression to Grade 4 rate is greater than 7.5% is  $> 80\%$ ; or observation of any grade 5 CRS after the event has been treated with siltuximab. The stopping boundaries presented below assume a prior distribution of Beta (0.4, 1.6) for progression to grade 3 CRS and a prior distribution of Beta (0.15, 1.85) for progression to grade 4 CRS. The evaluations could occur more frequently if necessary to address emerging safety concerns. If the triggered adhoc DLRM coincide with regular DLRM, they may be combined.

Number of Subjects Treated with Siltuximab	Trigger DLRM if severity of any CRS event treated with siltuximab progresses to Grade 5	
	Or this number of subjects with severity of CRS progressed to Grade 3 after being treated with siltuximab	Or this number of subjects with severity of CRS progressed to Grade 4 after being treated with siltuximab
5	$\geq 3$	$\geq 2$

10	≥ 4	≥ 2
15	≥ 5	≥ 3
20	≥ 6	≥ 3
25	≥ 7	≥ 4
30	≥ 9	≥ 4
35	≥ 10	≥ 5
40	≥ 11	≥ 5

[figure not shown]
CRS = cytokine release syndrome; DLRM = dose level review meeting.

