**Event with missing/unknown relationship to treatment will be assumed to be treatment-related.**

#### Dose Limiting Toxicities (DLT)

A DLT will be defined as any of the events described in protocol section 6.2.1.3 occurring in a subject during the DLT window. The DLT window will start on D1 (start of the administration of the first dose) and last for 28 days for all cohorts. Any adverse event occurring outside the DLT window that is determined by the investigator to be possibly related to the investigational product, which is seen more frequently or is more severe than expected or is persistent despite appropriate management, can be determined to be a DLT upon unanimous decision by the DLRT after review of the adverse event and all available safety data. Investigators will determine whether an adverse event qualifies as a DLT per protocol Section 6.2.1.3 and it will be collected by the flag indicating DLT in Events CRF.

Maximum Tolerated Dose (MTD)

The MTD is defined as the highest dose level whose DLT rate has the highest probability of the target TPI, an excessive/unacceptable TPI of < 0.25, and a minimum of 6 subjects have been treated at the MTD.

Overall Response (for R/R AML)

Overall response is defined as any of the following: complete remission (CR), CR with incomplete recovery (CRi), morphologic leukemia-free state, partial remission (all according to Revised International Working Group [IWG] response criteria) or CR with partial hematologic recovery (CRh).

Duration of Response (DOR) (for R/R AML)

Duration of response is defined as the number of days between the date of the first disease assessment indicating an overall response through the subsequent date of progression or relapse as defined by revised IWG response criteria or death due to any cause, or where applicable date of censoring [date of first progressive disease assessment or relapse or death or date of censoring – date of the first objective response result +1]. Subjects who respond and have not progressed or relapse or died while on study will be censored at the last adequate disease assessment date. Subjects who do not achieve an overall response will be excluded from the analysis of duration of response.

MRD Conversion Rate

MRD conversion rate is the number of subject achieve MRD- among subjects at who are MRD+ at enrollment. [REDACTED]

Overall Survival

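### The expansion pause table counts DLT events, but its limits and operating characteristics hold only if each subject counts once

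*SAP*

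**What the plan says.** SAP 3.3 gives the decision rule: "enrollment to dose expansion will be halted if the posterior probability that the DLT event rate is greater than 20% is > 80" per cent. It then states: "The stopping boundaries assuming a prior distribution of Beta (0.40, 1.60) are presented in" Table 1, with looks in a "pre-specified batch size of 6 new subjects per batch".

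Table 1 sets a number of subjects against a count headed "Pause study enrolment if observing the number of these many DLT events". Protocol 10.3, Table 26, has the same limits and the header "Pause study enrollment if observing the number of these many DLT events". SAP Table 2 and Protocol Table 27 give the operating characteristics.

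On data capture, SAP 5 says that the investigator decides whether an adverse event is a DLT and that "it will be collected by the flag indicating DLT in Events CRF".

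Two other places use a different unit. The siltuximab table in SAP 3.3, with the same prior for grade 3 progression and the same 20%/80% rule, is headed "Or this number of subjects with severity of CRS progressed to Grade 3 after being treated with siltuximab". SAP 9.6.1 and Protocol 10.5.2 fit the BLRM to the subject incidence of DLTs.

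**The concern.** A Beta prior updated with x out of n needs one yes/no outcome per subject. A count of events is a different quantity, because one subject can contribute more than one. The DLT list in Protocol 6.2.1.3 covers CRS, liver injury, non-hematologic toxicity and prolonged neutropenia, so two distinct DLTs in one subject are possible. A subject may also continue at a lower dose after a DLT under stated conditions, and later events can be declared DLTs by the DLRT.

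If the DLRT applies the header as printed, two things follow. Enrolment can be paused when the plan's own 80% criterion is not met. The pause probabilities and mean sample sizes in Table 2 then no longer describe the rule in use.

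**Working it through.** **Inputs.** Prior Beta(0.40, 1.60), rate limit 20%, probability threshold 80% and looks every 6 subjects (SAP 3.3). Maximum N is 40 for R/R ("FIH (R/R AML): approximately 40 subjects") and 50 for MRD+ (SAP 3.2).

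**Step 1: reproduce the limits.** Let x be the number of subjects with a DLT among n. The limit is the smallest x with P(p > 0.20 | Beta(0.4 + x, 1.6 + n − x)) > 0.80. The last column is the posterior when the number of DLT subjects is one below the limit.

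| n | Printed limit | Recomputed limit | Posterior at limit | Posterior one DLT subject below |
|---|---|---|---|---|
| 6 | 3 | 3 | 0.914 | 0.707 |
| 12 | 4 | 4 | 0.821 | 0.608 |
| 18 | 6 | 6 | 0.883 | 0.747 |
| 24 | 7 | 7 | 0.831 | 0.688 |
| 30 | 9 | 9 | 0.885 | 0.783 |
| 36 | 10 | 10 | 0.848 | 0.740 |
| 42 | 11 | 11 | 0.812 | 0.700 |
| 48 | 13 | 13 | 0.865 | 0.778 |

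All eight agree when x counts subjects.

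**Step 2: reproduce Table 2.** An exact binomial recursion over the looks (R/R 6 to 36, MRD+ 6 to 48), with at most one DLT per subject, gives every row to rounding. At a true rate of 0.10 it gives 3.8% and mean N 38.9 (R/R), and 3.9% and 48.5 (MRD+). At 0.20 it gives 34.0% and 31.5, and 37.8% and 37.8. Table 2 therefore assumes that each subject counts once.

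**Step 3: a case where the readings differ.** At n = 6, two subjects have a DLT and one of them has two flagged events. The event count is 1 + 2 = 3, so the table says pause. The posterior for 2 of 6 is 0.707, below 0.80, so the rule says continue. The last column above shows the same conflict at every look, with posteriors from 0.608 to 0.783.

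**Step 4: size, under an assumption.** The documents give no rate of repeat DLTs. Suppose a share s of DLT subjects have exactly two flagged events and the rest have one. Events per subject are then 0, 1 or 2 with probabilities 1 − p, p(1 − s) and ps. Running the same exact recursion against the printed limits gives these pause probabilities:

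| s | R/R, p = 0.10 | R/R, p = 0.20 | MRD+, p = 0.20 |
|---|---|---|---|
| 0 (Table 2) | 3.8% | 34.0% | 37.8% |
| 5% | 5.9% | 40.1% | 44.6% |
| 10% | 8.0% | 45.7% | 50.8% |
| 20% | 12.3% | 55.5% | 61.4% |
| 30% | 16.6% | 63.5% | 69.8% |

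**The case against.** The best reply is that this is loose wording with one sensible reading. The governing rule concerns a rate, the first column of the table counts subjects, the BLRM uses subject incidence, and the siltuximab table counts subjects under the same prior and thresholds. These passages do suggest that per-subject counting was intended. None of them governs the pause table, however. The text that does speaks of a DLT event rate in SAP 3.3 and in the opening of Protocol 10.3, although the decision sentence in Protocol 10.3 says DLT rate.

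A second reply is that double flags may be rare. Investigators record a diagnosis or syndrome where known (Protocol 9.2.1.1), so organ signs of CRS need not become separate events. Some grade 3 transaminitis with CRS is exempt. A DLT normally ends treatment, with continuation at a lower dose as a conditional exception (Protocol 6.2.1.4). This stands as a limit on the size, which is why the share of repeat DLTs is shown as an assumed range.

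A third reply is that the consequence is mild. A crossed limit leads to a pause and DLRT review, which may reopen enrolment, and any error is in the cautious direction. This also stands.

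A reader might infer three stronger things that the documents do not support:

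- That the limits are miscalculated. They are not; only the unit in the header is wrong.
- That one subject with two flagged events can pause enrolment alone. The lowest limit is 3, so that subject matters only when the number of DLT subjects is already one short.
- That the DLT criterion of two separate grade 3 CRS events shows double counting. It combines two events into one DLT.

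**Conclusion.** The point holds as a mismatch of units. The printed limits and Table 2 are right for subjects with at least one DLT, and the header tells the DLRT to count something else. Read literally, the table can call a pause at a posterior of 0.61 to 0.78, short of the stated 80%.

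That this conflict can arise follows from the documents and exact arithmetic. How often it would arise does not. With 5% to 30% of DLT subjects assumed to have exactly two flagged events, the R/R pause probability rises from 3.8% to 5.9%–16.6% at a true rate of 10%. At 20% it rises from 34.0% to 40.1%–63.5% (R/R) and from 37.8% to 44.6%–69.8% (MRD+). It would be too strong to say that enrolment will be paused too often: that depends on this share and on the DLRT counting literally. The harm is limited to extra pauses that can be lifted, and to a Table 2 that does not describe the rule as printed. It is worth correcting because a pre-specified pause rule applied by investigators and clinical staff should not rely on inference.

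**What to change.** 1. In SAP Table 1 and Protocol Table 26, change the count column to the number of subjects with at least one DLT.
2. In SAP 3.3 and Protocol 10.3, replace the DLT event rate by the proportion of subjects with at least one DLT.
3. Add one sentence to each stating that a subject counts once for the pause rule, however many events are flagged.

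The limits, Table 2 (Protocol Table 27) and the sample size stay as they are, so the cost is a wording change in both documents. A subject with several DLTs gets no extra weight in the formal rule, but continual DLRT review of all DLTs and the ad hoc safety meetings still cover such a subject.

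This change need not also fix the denominator as DLT-evaluable subjects. Protocol 3.4 requires replacement of non-evaluable subjects only during escalation, so that denominator could move the expansion looks off the 6, 12, … grid on which Table 2 was computed. If the sponsor wants it, it should be considered separately.
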